5.2. Related research

A significant amount of research has been undertaken in the field of acoustic detection of aspiration. This stems from the longstanding use of stethoscopes to listen to the throat as a crude test of swallowing disorders. A full review of the literature was conducted prior to embarking on this project, and two existing reviews were also identified.

The first review by Dudik *et al.* (2015)¹⁶ is very relevant to our work, providing an overview of cervical auscultation (the recording of sounds and vibrations from the throat) and signal processing techniques. The studies identified in the review provide a useful foundation for our work, establishing variables that may affect swallow sounds (e.g. food consistency), and investigating the impact of microphone position on the neck on the recordings obtained. No studies included in the review or identified in our own literature review have used multiple microphones to record sounds in an array. The review concludes that the addition of objective methods of data analysis has enhanced the diagnostic process, but that consensus on the best signal processing technique has not been reached. Signal processing to date has remained relatively basic, and has not integrated more than one type of sensor input.

The second review (2013) assesses the current evidence for the clinical assessment of aspiration following stroke¹¹, which is one of the leading causes of dysphagia. Non-instrumental assessment techniques ('bedside' tests e.g. the water provocation test) are comprehensively considered, finding that none have acceptable sensitivity and specificity to ensure accurate detection of aspiration. Regarding videofluoroscopy, evidence assessed in the review supports the technique as the best currently available for detecting silent aspiration, while noting the following disadvantages: i) The procedure is relatively complex, time consuming and resource intensive; ii) there is some exposure to radiation; iii) the test is not appropriate for some patients who may have difficulty in sitting upright in a chair. The results of the test can also be difficult to interpret and there can be significant variation among individual raters. The review states that limited evidence exists for pulse oximetry, leaving the association between aspiration and oxygen desaturation as inconclusive.

In addition to the reviews, two studies stand out as particularly relevant. The first was published by Shirazi *et al.* in 2014⁷. This group used a single microphone to record an increase in turbulent air flow within the trachea in response to a foreign body from aspiration. Analysing acoustic recordings with relatively basic signal processing techniques provided a sensitivity of 91% and specificity of 85%. We hope to build on this work by using multiple acoustic channel recording and combining this with pulse oximetry recording. The multi-channel approach in theory will improve signal detection and aid in the removal of background noise.

Relatively little work has focused on a paediatric population, and the second paper of note focuses on the joint analysis of swallow and breath sounds in children with a mean age 24 months¹⁷. Using an optimal combination of parameters relating to swallow and breathing sounds an accuracy classifying swallows as aspirating of 82% was achieved.

The above work provides a strong foundation for our study, which will investigate if a microphone array, combined pulse oximetry, complex signal processing and a focus on tracheal air flow can improve the classification of swallows as safe or unsafe.

6. Plan of the investigation

6.1. Methodology

Preliminary testing / Public and patient involvement

The team has agreement to access a database held by Sheffield Teaching Hospitals NHS FT of individuals who have or have had dysphagia, and who have consented to support the development of research studies. This database will be used to identify potential invitees for a focus group discussion. Refreshments will be provided and travel arranged/travel costs reimbursed. We hope to form a group of 6-8 patients and carers to discuss:

- their experiences of current screening and diagnostic options
- an outline explanation of the aims of this project
- discussion of any perceived benefits/challenges to any potential trial participants
- opportunity to see and try the proposed aspiRATE equipment

A clinician known to database members (but not a member of the research team) will send out the initial invitation letter. She will also host the group along with one person from the research team. We aim for a relaxed and open discussion in order to gain valuable feedback on the important considerations for users in any testing, and specific comments on the proposed study design. The team will be open to suggestions regarding modifications that may make the trial more user-friendly. The equipment array will be fitted to volunteers from the user group at this event to gain feedback on comfort and acceptability.

Clinical trial

The trial can be considered in two parts:

- Part 1, which will focus on tolerability during videofluoroscopy and ensure that there is no adverse impact on the usual clinical care
- Part 2, where dedicated trial staff will collect data with the equipment array alongside standard clinical care.

Part 1. The primary aim of part 1 of the trial is to ensure that the equipment array can be used alongside videofluoroscopy in a manner that doesn't impede the clinical utility of the examination. It will allow technical and radiology staff to familiarize themselves with performing the study protocol, additional time will be allowed for each of these procedures, in order to reduce time pressure and members of the research team will be on hand for support. We envisage 3-5 patients should be a sufficient sample to complete this first phase.

Eligible patients will be identified by the Speech and Language Therapy team at Sheffield Teaching Hospitals NHS FT. These will be patients who are known to experience at least occasional

aspiration, following initial videofluoroscopy as part of their usual clinical care.

Patients requiring follow up videofluoroscopy (either to check for deterioration or progress made in response to swallow therapy) will be sent a letter inviting them to their follow up appointment and explaining that they have the opportunity to participate in a research study on a voluntary basis. The letter will contain a patient information sheet explaining the study, and what participation will involve. Patients who express an interest in participating in the study they will be booked a double-length appointment to allow sufficient time for any delay that research participation may involve.

At their appointment the patient will be met by a research nurse and a study technician. The nurse will explain the study again, answer any questions and take written informed consent for study participation. The patient will have the option of declining to participate in the study with no effect on the planned videofluoroscopy study and ongoing clinical care.

The videofluoroscopy study will be performed in the standard manner, by two appropriately qualified Speech and Language Therapists and a Radiographer. In addition the aspiRATE equipment array will be attached by a study technician, in order to capture the additional data for the study so that it can be validated against the videofluoroscopy assessment.

Patients involved in Part 1 of the study will be asked to feedback on the design of the aspirate device, in particular the neck attachments. The radiographer performing the study will also be asked for feedback on the use of the device during videofluoroscopy, in particular to identify any hindrance to the acquisition or interpretation of images.

Once it has been confirmed that the equipment array can be easily applied, and does not interfere with standard videofluoroscopy, Part 2 of the study will be started. If it is found that the equipment array interferes with videofluoroscopy, progression to Part 2 will be halted until the issues are resolved.

Part 2. The primary aim of Part 2 of the trial is to collect data from a group of dysphagic patients using the proof-of-concept aspiRATE equipment array, allowing signal processing experts to develop the required multi-sensor analysis algorithms.

We aim to recruit up to 45 patients with dysphagia, according to referral rates within the timescale of the trial to the standard videofluoroscopy clinics within STH.

We will aim to recruit consecutive patients in one of three cohorts

1. Dysphagia with no aspiration
2. Dysphagia with clinically detectable aspiration (coughing, wet voice)
3. Dysphagia with silent aspiration

Potential trial participants will again be identified by the Speech and Language Therapy team at Sheffield Teaching Hospitals NHS FT. Once again a letter inviting trial participation will be sent, with a patient information leaflet enclosed.

On attending the clinic, the patient will be met by a research nurse to ask if they are interested in finding out more about the study. The nurse will explain the study again, answer any questions and take written consent for study participation. A study technician will attach the equipment array prior to the videofluoroscopy assessment, and be present to assist the radiographer if needed. Acoustic recordings and pulse oximetry data will be collected during the videofluoroscopy examination with no change to the standard protocol. The patient will be asked for feedback and their involvement in the trial will finish at the end of the clinic appointment.

For the purpose of the study videofluoroscopy findings will be interpreted using the Rosenbek Penetration-Aspiration Scale¹⁸, and acoustic and pulse oximetry recordings from aspirating and non-aspirating swallows will be compared by signal processing experts to identify any characteristic

features in those where aspiration occurred.

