6.8. Analysis including statistical methods

[figure not shown]
Anonymized data (from both the equipment array and the videofluoroscopy) will be examined by the research team. Standard methods of analysis will be applied to acoustic recordings to assess the differences between those from aspirating and non-aspirating patients, and to compare these findings with the aspirating and non-aspirating videofluoroscopy data. An auditory processing algorithm that can be applied to future recordings will be developed.

Data from the device (index test) and videofluoroscopy (reference standard) will be used to populate a standard 2x2 table, allowing calculation of the device sensitivity and specificity. Receiver Operating Characteristic (ROC) curve analysis will allow refinement of the signal processing algorithm and interpretation thresholds, although as a screening test false positives will be considered preferable false negatives.

[figure not shown]
6.9. Intervention:

Patient Pathways

Part 1 Trial

Part 2 Trial

Flow chart indicating participant's involvement throughout the course of the study

6.10. Safety assessment:

The following issues have been considered as part of the risk assessment process of the new equipment array.

- Device obscures visualization of swallow on videofluoroscopy due to inadequate radiolucency – Videofluoroscopy assessments will be conducted by speech and language and radiography professionals, and initial testing (part 1 trial) includes built-in time to allow

the device to be adjusted or modified to improve videofluoroscopy views. In individual patients testing will be terminated early if inadequate views can be obtained for clinical use.

- Equipment prevents adequate patient positioning for videofluoroscopy – The attachment of the equipment attachment will be designed in conjunction with Speech and Language Therapists ensuring that it should not prevent the expected patient positioning. Initial PPI and the Part 1 trial are designed to allow refinement of the design if positioning proves problematic. In individual patients testing will be terminated early if positioning is inadequate for clinical use.

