- Patient aspirates during videofluoroscopy – Aspiration is expected in some patients during videofluoroscopy and the risk should not be increased by use of the new equipment array. Most episodes of aspiration during videofluoroscopy have no sequelae. The equipment will be easy to remove and will not interfere with the provision of supportive treatment after aspiration in the unlikely event this is required.
- Radiation exposure – All participants in this study will already be undergoing videofluoroscopy for clinical reasons. In a limited number of cases, during the examination (which required multiple swallows to be performed) additional swallows may be requested to provide data for use only in the trial. The recording of any additional swallows would expose the patients to small amounts of ionizing radiation. This risk has been assessed by [name], Head of Radiology Physics and Radiation Protection Adviser at Sheffield Teaching Hospitals NHS FT.
- Electrical shock risk – Only the low voltage microphones and pulse oximetry probe will make contact with the patient. The equipment array will be assembled and checked by medical engineering professionals to meet EU medical device safety standards.
- Allergy to medical adhesives used to attach the microphones – standard echo cardiology sensors will be used with additional measures as per individual patient need
- Infection control risk. All research project equipment which would contact patients' skin will be for disposal single patient use. Research project equipment which will not be in contact with patients' skin and the usual videofluoroscopy equipment will be sanitized according to Sheffield Teaching Hospitals Infection Control guidance.
- The protocol has received scientific review from [name], Royal College of Speech and Language Therapy Advisor in Dysphagia (Manchester) and Clinical Lead in Dysphagia University Hospital South Manchester NHS Foundation Trust.

Adverse events will be discussed at pre-existing institutional audit sessions, and reported online using standard STH incident report forms. In addition regular meetings of the study steering committee (co-investigators and CUHP representative) will allow further discussion. If a concern arises regarding device safety recruitment will be suspended until the risk has been mitigated.

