- The target population includes vulnerable adults who may be suffering from cognitive impairment. Some patients may lack capacity to consent. – Only nurses trained in informed consent will discuss the project with patients and obtain written consent. If there is a concern that patients lack adequate capacity they will be excluded from study.
- Patients will only have a short period to consider trial involvement after speaking to the research nurse on the day of their clinic. – Information sheets using lay language and large font will be sent out with the invite letters to ensure that patients have the opportunity to discuss information with family members if they wish, in order to start the nurse-led discussion with a basic understanding of the trial. Contact details will be available in the information leaflet to allow interested patients to further discuss the trial with a member of the study team prior to the day of testing. It will be made clear that consent may be withdrawn at any point without detriment to care.
- The attachment of the aspiRATE equipment array could lead to discomfort – The equipment will be ergonomically designed from soft materials where possible to improve comfort and reduce the bulk of the attachment. Prior to clinical studies the equipment will be attached to

members of the target population during a PPI focus group event. Feedback will be obtained and the device modified if required to improve comport. Feedback on comfort will also be collected during clinical trials.

- All videofluoroscopy assessments will be arranged due to clinical need. Patients may be asked to repeat swallows for the purpose of additional acoustic recording, however trials will be supervised by a qualified Speech and Language therapist and a Radiographer and if the patient is felt to be at risk the device testing will be terminated. This is in line with usual practice during videofluoroscopy studies. Radiation risk assessment has been completed by [name], Head of Radiology Physics and Radiation Protection Adviser at Sheffield Teaching Hospitals NHS FT.

11. Service users

The project has been initiated by Speech and Language and Medical staff who meet with service users suffering from dysphagia and aspiration on a regular basis. It has been noted that there is a clear concern from clinical staff and service users that currently there are limitations to the reliability and accessibility of diagnosis and monitoring of swallow safety.

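### Does the assurance that Part 2 leaves the standard videofluoroscopy protocol unchanged conflict with the allowance for extra swallows recorded only for the trial?

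*Protocol*

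**What the plan says.** Three places in the Protocol bear on this.

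- **Section 6.1, Part 2**, describing the clinic visit: "Acoustic recordings and pulse oximetry data will be collected during the videofluoroscopy examination with no change to the standard protocol".
- **Section 6.10, radiation item.** It begins: "All participants in this study will already be undergoing videofluoroscopy for clinical reasons". It then says that in a restricted number of patients "additional swallows may be requested to provide data for use only in the trial", and acknowledges the consequence: "The recording of any additional swallows would expose the patients to small amounts of ionizing radiation". It records that the radiation protection adviser has assessed this risk.
- **The list that ends just before section 11 (Service users).** "Patients may be asked to repeat swallows for the purpose of additional acoustic recording". The same sentence puts this under a qualified speech and language therapist and a radiographer, and ends device testing if the patient is thought to be at risk. The next sentence describes this as normal videofluoroscopy practice, and the item closes by citing the radiation risk assessment again.

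Section 6.5 plans 20 to 45 participants for Part 2, and section 6.13 gives the same range.

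**The concern.** A swallow under X-ray that is requested only to give the trial data is something the patient would not otherwise undergo. The Part 2 description in 6.1 says nothing in the examination changes, while the safety section and the later list say that something may. A technician or radiographer who reads only 6.1 would conclude that research swallows are not part of Part 2. One who reads only 6.10 would conclude that they may be requested.

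The text does not obviously confine the extra swallows to Part 1. Two other items in 6.10 name Part 1 when they describe something particular to it: "initial testing (part 1 trial) includes built-in time to allow" and "Initial PPI and the Part 1 trial are designed to allow refinement of the design if positioning proves problematic". The radiation item does not.

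If the conflict were real, two things would be at stake. The first is whether research-only radiation is authorised for Part 2 patients. The second is whether the safety text covers it, because the 6.10 assurance about aspiration risk concerns the equipment and not additional swallows. A statistician would also ask whether extra swallows could change which group a patient falls into (6.5) or which cell of the two-by-two table (6.8).

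**Working it through.** The Protocol gives no figure to reproduce here, so the check is a comparison of texts.

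**1. Do the sentences refer to the same thing?** Section 6.1 outlines the ordinary Part 2 visit. Section 6.10 lists risks and how each is handled. Its sentence on extra swallows is permissive and limited to some patients, within an examination that it says already needs several swallows. A general description in one section and a disclosed exception in another can stand together. What 6.1 lacks is a pointer to the exception.

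**2. Which part of the trial do the extra swallows belong to?** The visible text does not say.

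| Clue | What it supports |
|---|---|
| "All participants in this study will already be undergoing videofluoroscopy for clinical reasons" | Little. It says everyone has a clinical indication; it is not the sentence that permits extra swallows. |
| Two other 6.10 items name Part 1 | Little. They concern adjusting the device, which is Part 1's task, so silence elsewhere need not mean both parts. |
| Part 1 patients get double-length appointments (6.1) | Makes a Part 1-only reading possible, but the reason given is delay, not more swallows. |
| Part 2's main purpose is data collection (6.1) | Makes a Part 2 reading at least as plausible. |

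The patient pathway charts in 6.9, which show participants' "involvement throughout the course of the study", and the opening of the list before section 11 were not visible in the copy reviewed. Either could settle the scope.

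**3. Is the exposure hidden or unmanaged?** No. It is disclosed and described as small in 6.10, and its risk assessment is cited there and again before section 11. Supervision and a stopping provision stand in the very sentence that permits the repeats.

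**4. How many patients, and how much exposure?** The conflicting sentence concerns Part 2, so 20 to 45 planned participants is the outer bound. The Protocol gives no number of patients asked, no number of swallows and no dose. Neither the number affected nor the added exposure can be calculated.

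**5. Could it distort the results?** Groups are allocated after the examination from the videofluoroscopy (6.5). Additional swallows recorded under X-ray have both the device signal and the reference reading, so an extra swallow adds a paired observation. It could move a patient from the non-aspirating to an aspirating group, but the reference would then show what actually happened on that swallow. Section 6.5 also states that establishing diagnostic accuracy is not the aim of this work. No bias is shown.

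**The case for a change.** The strongest case for acting is that 6.1 is the section staff work from in Part 2, and on its face it excludes what 6.10 permits. Research-only radiation is not a matter on which staff should have to choose between sections. The sentence about normal practice before section 11 does not dispose of this. It may refer only to supervision and stopping, and even if it covers repeats, 6.10 still describes the additional swallows as serving the trial alone. Aligning the text would cost a few words.

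Part of that stands. The literal mismatch is real, the scope is unstated in the visible text, and the aspiration item in 6.10 does not itself address additional swallows. Calling the statements incompatible goes too far, because a limited and openly stated exception is an ordinary way to write a safety section. The safety argument is also largely met, since supervision and stopping are attached directly to the repeats. Marking every trial-only swallow in the recording log would be a preference, because no bias has been shown that the mark would detect or remove.

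**Conclusion.** This is a clerical inconsistency that calls for no change to the plan. The general statement in 6.1 and the exception in 6.10 can be read together, and the extra exposure is disclosed, risk-assessed and supervised. The wording could be reconciled by a cross-reference whenever the Protocol is next edited. That would leave trial conduct, radiation exposure, group allocation and conclusions as they are. This review takes no view on which statement about extra swallows should govern.

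The issue touches at most the 20 to 45 Part 2 participants, in an unstated number of whom extra swallows might be requested, with no demonstrated effect on results or on safety. The conclusion assumes that the 6.10 sentence is meant as an exception to the ordinary visit, and that the pathway charts and the unseen opening of the list before section 11 say nothing to the contrary.
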